## Overview of Study Design and Key Features

### Part B

Design Features	
 
Multi-country, multi-center.
 
Intended duration of the study per participant: Approximately 6 months.
 
Aspects of data collection: blood samples, safety events.
 
Method of data collection:           
 
Standardized electronic Case Report Form (eCRF)
 
Solicited AEs that occur during the 7-day follow-up period after study intervention will be collected using an electronic Diary (eDiary). Unsolicited AEs will be collected using eCRF.
 
 
 
Safety monitoring: the continual review of safety data will be performed by an unblinded IDMC and a blinded SRT. An unblinded iDRC will review safety (and immunogenicity) data from the Day 29 interim analysis to make recommendations for a future Phase 3 study: Part A - on dose selection and PartB – on storage condition. Refer to Section 8.4 of the protocol for more information on safety monitoring strategy applicable to this study and Section 8.5 of the protocol for IDMC, SRT and iDRC composition and role.
 

Study intervention	
 
Part A: The study interventions administered in part A of the study include the CV0701 bivalent vaccine, CV0601 monovalent vaccine and comparator vaccine CCI
 
Part B: The study intervention administered in part B of the study is the CV0801 monovalent vaccine under 3 different storage conditions baseline control (condition 1), intermediate (condition 2) and maximum storage (condition 3) condition.
 
All study interventions are administered as single-dose intramuscularly (IM).
 

Study intervention Assignment	
 
Part A: Participants will be randomly assigned (1:1:1:1:1) to the study groups using a central randomization system. The randomization will be based on permutation blocking scheme using country, previous known COVID-19 (yes, no), and age (< 65 years, ≥65 years) as stratification factors.
 
Part B: Participants will be randomly assigned (1:1:1) to the study groups using a central randomization system. The randomization will be based on permutation blocking scheme using country, previous known COVID-19 (yes, no), and age (< 65 years, ≥65 years) as stratification factors.
 

Interim Analysis	
 
For Part A and Part B separately, interim analysis will be performed based on safety and immunogenicity data (neutralization titers matched to the variant encoded on the study vaccines) for all participants up to Day 29.
 
Additional analyses e.g., safety analyses, will be conducted to support IDMC and SRT decisions.
 

## 2. STATISTICAL HYPOTHESES

There is no hypothesis testing in this study; where statistical methods are applied, the emphasis will be on estimation with 95% confidence interval (CI). To provide preliminary evidence of non-inferiority, p-values for the null hypothesis that the group GMT ratio (investigational group over the control group for Part A; Conditions 2 and 3 groups over Condition 1 group for Part B) is below 0.67 will be provided for the immunogenicity primary endpoints (see Section 4.2.2).

### 2.1. Multiplicity Adjustment

As this study is descriptive, no adjustment for type 1 error will be done.

## 3. ANALYSIS SETS

**Table 1 Analysis set definition and analyses evaluated**

Analysis Set	Definition / Criteria	Analyses Evaluated
Enrolled	
 
All participants who entered the study (who were randomized or received study intervention or underwent a post-screening procedure)
 
 
NOTE: screening failures (who never passed screening even if rescreened) and participants screened but never enrolled into the study (Met eligibility but not needed) are excluded from the Enrolled Analysis set as they did not enter the study.
	
 
Study Population
 

Exposed Set (ES)	
 
Participants who received study intervention
 
Participants will be analysed according to the study intervention administered.
 
	
 
Safety, immunogenicity if applicable, demography
 

eDiary Set	
 
All participants in the Safety analysis set for whom eDiary data are available (complete or partial).
 
	
 
Solicited AEs
 

Per-Protocol Set (PPS)	
 
All participants from the ES who were eligible, complied with vaccination as per protocol (e.g., vaccine not expired, with appropriate temperature storage), and had a pre-dose and Day 29 anti-neutralizing titer against either the CCI [REDACTED] CCI [REDACTED] strains.
 
 
Immunogenicity data at a post-vaccination visit will be censored in case of noncompliance for the blood sample visit. Likewise, immunogenicity data after the following intercurrent event will be censored: COVID-19, immunosuppressive or immunodeficient conditions, COVID-19 vaccination and prohibited medication/vaccination after study intervention.
	
 
Immunogenicity, demography
 

## 4. STATISTICAL ANALYSES

### 4.1. General Considerations

All statistical analyses will be performed using SAS® software Version 9.4 or later. Part A and Part B will be analyzed independently, the considerations outlined in this SAP apply separately to each part unless stated otherwise.

Missing data will not be imputed unless mentioned otherwise (refer to Section [6.2.2](#)).

#### 4.1.1. General Methodology

Enrolled participants who withdraw from the study will not be replaced.

Continuous data will be summarized using descriptive statistics (n, mean, standard deviation, median, quartiles, minimum, and maximum). Categorical data will be summarized using the participant count and percentage for each category.

[figure not shown]
A row denoted “Missing” will be included in count tabulations where specified on the shells to account for dropouts and missing values.

The denominator for all percentages will be the number of participants with non-missing values of corresponding parameter in that study group within the analysis population of interest, unless otherwise specified.

Confidence intervals (CIs) will use 95% confidence levels.

For calculations regarding antibody levels/titers descriptive statistics will also be provided i.e. number of evaluable samples, geometric mean titer (GMT) and geometric mean increase (GMI) (and the associated geometric standard deviations), median, quartiles, minimum, and maximum and 95% CI. Geometric means are calculated by obtaining the mean of the log10 titers and then back transforming to the original scale. Geometric standard deviations (SDs) are calculated as  $10^{(\text{standard deviation of log10 titers})}$ . CIs are calculated using t-distribution of log transformed values then back transformed to the original scale. Antibody values reported as below the LLOQ or a quantifiable threshold will be replaced, respectively, by half the LLOQ or by half the threshold while values above a quantifiable threshold will be assigned the value of the threshold. For neutralization assays **CCI** [REDACTED], the value of the LLOQ is 10. The percentage of participants with titer above the LLOQ will also be provided per variant per time-point.

CCI

CCI

A listing (TLF) is to be generated on the enrolled set for any required item even where no data is available or reported. In such cases, the listing will state: "No Data Reported".

#### **4.1.2. Baseline Definition**

Baseline will be defined as the last non-missing evaluation prior to study intervention administration, unless otherwise specified.

### **4.2. Primary Endpoint(s) Analyses**

#### **4.2.1. Safety and reactogenicity endpoints**

For Part A and Part B separately, reactogenicity descriptive summary statistics will be provided for the eDiary Set by vaccine group; other safety endpoints, descriptive summary statistics will be provided for the ES.

##### **4.2.1.1. Solicited AEs**

All solicited events must be recorded into the eDiary by the participant during the first 7 days following administration of the dose of study intervention (Day 1 to Day 7 included), irrespective of occurrence or intensity. Solicited events ongoing after Day 7 will be recorded in the eCRF and followed-up until the event has resolved, subsided, stabilized, disappeared, or until the event is otherwise explained, the participant is lost to follow up, or study is completed. If the collection of solicited AEs was not possible for any reasons via the eDiary and solicited AEs were reported to the investigator by the participant, then it would be possible for them to be reported directly to the site staff and submitted (e.g., via the eCRF).

The following administration site events will be solicited:

- a. Pain
- b. Redness
- c. Swelling
- d. Lymphadenopathy, defined as localized axillary, cervical or supraclavicular swelling or tenderness ipsilateral to the injection arm

The following systemic events will be solicited:

- e. Fever
- f. Chills
- g. Headache
- h. Fatigue

- i. Myalgia
- j. Arthralgia

Note: Participants will be instructed to measure and record the axillary temperature in the evening. If additional temperature measurements are taken at other times of the day, participants will be instructed to record the highest temperature in the eDiary.

Grading or actual temperature/redness and swelling will be captured in the eDiary as per a modified grading of symptoms based on the FDA toxicity grading guidance for industry [FDA, 2007] with Grades 3 and 4 combined and swelling evaluated using the actual measurement only (refer to Section 6.2.2.2). When solicited AE data entered by the participant are missing or incorrect, data collected by study investigator/staff will be used in the summaries if available.

The percentage of participants reporting each individual solicited administration site event (any grade, Grade 1, Grade 2, Grade 3, any grade ongoing at day 7 and medically attended events) and solicited systemic event (any grade, Grade 1, Grade 2, Grade 3, any grade ongoing at day 7 and medically attended events) within the 7-day follow up period (i.e., Day 1-Day 7 post-dosing) will be tabulated for each group.

The duration of solicited AEs of any grade (see Section 6.2.1.10) will be summarized. The start date is the first day during the 7-day solicitation period with the symptom at grade > 0 while the stop date is the last day with the symptom at grade > 0 in or beyond the solicited period. In addition, the duration for specific grade(s) for each symptom defined as the number of days in the reporting period with grade above or equal to specific grade will be summarized.

Prolonged solicited AEs that continue beyond Day 7 or Day 28 will be identified using a flag in listing of AEs.

The percentage of eDiary days completed in the solicited period will be summarized by group. A day is considered completed in the eDiary if it was entered by the participant or the investigator. The percentage of completed days will be calculated as follows:

$$\text{SumSymp}/(7*\text{NumSymp}*\text{ExpSubj})$$

SumSymp is the sum of the total number of days completed for a specific symptom across all symptoms and exposed subjects. NumSymp is the number of symptoms and ExpSubj is the number of exposed subjects.

#### **4.2.1.2. Unsolicited AEs with onset within the 28 days follow-up period (day 1-28)**

An AE is any untoward medical occurrence in a clinical study participant, temporally associated with the use of a study intervention, whether or not considered related to the study intervention. An AE can therefore be any unfavorable and unintended sign (including an abnormal laboratory finding), symptom, or disease (new or exacerbated) temporally associated with the use of a study intervention.

The verbatim reports of unsolicited AEs will be reviewed by a qualified person and the signs and symptoms will be coded according to the Medical Dictionary for Regulatory Activities (MedDRA) Dictionary for Adverse Reaction Terminology. Every verbatim term will be matched with the appropriate PT.

A study intervention causally related AE is defined as an AE for which the investigator classifies the possible relationship to study intervention as “Yes”. Investigators will not be required to assess the causality of solicited Aes if the onset is during the solicitation period.

The investigator is obligated to assess the relationship between study intervention and each occurrence of each AE/SAE/. The investigator will use clinical judgment to determine the relationship.

The percentage of participants with any unsolicited Aes within the 28-day follow up period (i.e., Day 1-Day 28) with its exact 95% confidence interval (CI) will be tabulated by group and by MedDRA PT and System Organ Class (SOC). Similar tabulation will be done for Grade 3 unsolicited Aes, for any causally related unsolicited Aes, for Grade 3 causally related unsolicited Aes, for unsolicited Aes resulting in a medically attended visit and for SAE.

A data listing for all unsolicited AEs will be provided by age group (< 65 years,  $\geq$  65 years), dose group and participant number.

#### **4.2.1.3. MAAEs, SAEs and AESIs with onset after vaccination (day1 up to study end)**

The study will capture the following specific over the full study period: MAAE, SAE and AESIs defined as either :

- Potential immune-mediated disorders (pIMDs),
- Any laboratory-confirmed moderate to severe case of COVID-19,
- Myocarditis and pericarditis and,
- Anaphylaxis or severe hypersensitivity within 24 hours after study intervention administration.

All suspected cases of COVID-19, myocarditis, and pericarditis in study participants will be diagnosed and clinically evaluated, which may require unscheduled study site visits and additional testing based on the investigator’s judgment.

The number and percentage of participants with any event for each MAAE, SAE, AESI In addition, summary will be provided by relationship to study intervention, maximum grade/severity and outcome. The worst-case approach will be applied at participant level for the maximum grade/severity, i.e., a participant will only be counted once as the worst case from all the events experienced by the participant.

The percentage of participants with at least 1 report of SAE (any, related, fatal and fatal related), with at least 1 report of MAAE and with at least 1 report of AESI, respectively,

classified by the MedDRA SOC and PT and reported from Dose 1 up to study end will be tabulated with exact 95% CI.

In the AESI/SAE summaries, a participant with 2 or more Aes within the same SOC or PT level but different relationship will be counted only once in the level using the related incident.

#### 4.2.2. Co-primary and Secondary Immunogenicity Endpoints

All immunogenicity endpoints will be analyzed separately for Part A and Part B. Prior to the final study analysis, all primary endpoint immunogenicity analyses will be based on the ES (e.g. interim analysis, analyses to support IDMC and iDRC). At the final analyses immunogenicity will be based presented for both ES and PPS.

In part A, for each variant CCI [REDACTED] and at the specified time points the comparison of CV0701 and CV0601 booster vaccines with CCI [REDACTED] CCI [REDACTED] will be performed. In part B, each of Conditions 2 and 3 will be compared with Condition 1 at Day 29 with respect to CCI [REDACTED]. In both Part A and Part B, the comparisons will be obtained as follows:

The group GMT ratio, associated 2-sided 95% CI and p-value for the null hypothesis that group GMT ratio is below 0.67 will be based on group contrast from an ANCOVA model on log10-transformed anti-neutralizing titer. The model will include the vaccine group, country, previous known COVID-19 infection (yes, defined by self-reporting or positive N protein at pre-vaccination, no), age (< 65 years,  $\geq$  65 years), and log10-transformed pre-dose titer as fixed effects. The adjusted GMT and GMI in each group will be obtained from the same model with 95% CI. Missing data will not be replaced. For this model, a titer below LLOQ or a quantifiable threshold will be assigned, respectively, half the LLOQ or threshold while a titer above a quantifiable threshold will be assigned the threshold.

For each vaccine group the seroresponse rate will be provided together with 95% CI derived using the method of Clopper and Pearson [Clopper, 1934]. The 2-sided 95% CI on group difference in seroresponse rate between an investigational study intervention and (minus) the control group will be computed based on the method of Miettinen and Nurminen [Miettinen, 1985].

**Table 2 GMI and Seroresponse definition**

Abbreviation/term	Definition
GMI	The geometric mean of the ratios of the post-dose titer over the pre-dose titer.
Seroresponse rate	The percentage of dosed participants who have either a pre-dose titer < LLOQ and a post-dose titer $\geq 4 \times$ LLOQ or a pre-dose titer $\geq$ LLOQ and at least a 4-fold increase in post-dose titer.

The following SAS code will be used for computation of GMT ratio where 'log' and 'logbase' are the  $\log_{10}$  transformed values at post-dose and pre-dose respectively, 'trt' is

the vaccine group, while country, 'priorcovid' and 'agegroup' are the stratification factors at randomization:

```
PROC GLM DATA=is ALPHA=0.05;
  CLASS trt country priorcovid agegroup;
  BY visit istest variant;
  MODEL log = trt country priorcovid agegroup logbase;
  LSMEANS trt / CL;
RUN;
```

The seroresponse rate will be computed using the following SAS code where 'seroresp' is the seroresponse status post-dose:

```
PROC FREQ DATA=immuno;
  BY istest variant;
  TABLE trt*seroresp / RISKDIFF (CL=MN) ALPHA=0.05;
RUN;
```

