## 4.2. Scientific rationale for study design

### 4.2.1. Scientific rationale for study design for Part A

Interim data from the CV0501 Phase 1 study informs the study design of Part A (CV0701 and CV0601 Phase 2 study). This is founded on the basis that a similar safety profile can be expected as these investigational vaccines [REDACTED]

CC1 [REDACTED]

These 2 vaccine candidates will be compared against [REDACTED] CCI [REDACTED] which represents current standard of care, in a randomized, observer-blinded, and contemporaneously enrolled study. Part A of the Phase 2 study measures post-vaccination serum neutralization titers for its main immunologic endpoints. Post-vaccination neutralizing titers have been associated with COVID-19 vaccine efficacy in several analyses of [REDACTED] studies leading to vaccine authorization or licensure [Feng, 2021; Fong, 2022; Fong, 2023; Gilbert, 2022]. Vaccine efficacy increased with the neutralizing titer in each of these analyses of mRNA vaccines. These associations within a clinical study setting are additionally supported by meta-analyses of vaccine effectiveness within large populations, mechanistic biologic studies of nonhuman primates and therapeutic intravenous administration of virus neutralizing monoclonal antibodies.

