## 9.2. Analysis sets

The primary analysis of unsolicited AEs, MAAEs, SAEs, and AESIs will be based on the Exposed Set (ES), defined as data from all exposed participants.

The primary analysis of solicited AEs will be based on the Diary Set, defined as data from all exposed participants for whom diary data are available.

The primary analysis of immunogenicity will be based on the Per Protocol Set, defined as data from participants from the ES who were eligible, complied with vaccination as per protocol (e.g., vaccine not expired, with appropriate temperature storage), and had a pre-dose and Day 29 anti-neutralizing titer against either the **CCI** **CCI**. Immunogenicity data at a post-vaccination visit will be censored in case of noncompliance for the blood sample visit. Likewise, immunogenicity data after the following intercurrent event will be censored: COVID-19, immunosuppressive or immunodeficient conditions, COVID-19 vaccination and prohibited medication/vaccination after study intervention.

For all analyses, the study group will be defined by the vaccine administered at Visit 1.

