#### 4.3.1. Main analytical approach

The analyses of secondary endpoints at the specified time points will be performed as described in Section 4.2.2.

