### 5. SAMPLE SIZE DETERMINATION

#### Part A

Approximately 415 participants will be enrolled in the study and randomized in a 1:1:1:1:1 ratio to receive 1 of the 3 CV0701 formulations, CV0601, or the comparator vaccine (i.e., 83 participants will be enrolled in each of the 5 groups).

Part A will provide preliminary evidence of CCI

CCI  
CCI  
CCI  
CCI  
CCI  
CCI  
CCI

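### Part A Per-Protocol Set: Day 91 and Day 181 titers are analysed visit by visit among those not censored for COVID-19, which overstates late GMTs if low-titer participants are infected more often

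*SAP*

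**What the plan says.** - **Censoring.** Protocol Section 9.2 defines the PPS, names it as the primary set for immunogenicity, and says "immunogenicity data after the following intercurrent event will be censored: COVID-19, immunosuppressive or immunodeficient conditions, COVID-19 vaccination" (prohibited treatments follow in the list). SAP Section 3, Table 1 repeats this in the PPS row only. SAP Section 6.1.3 removes PPS data from the day of a SARS-CoV-2 infection onward.
- **Model.** SAP Section 4.2.2 fits an ANCOVA on log10 titer with group, country, prior COVID-19, age group and log10 pre-dose titer. The code below SAP Table 2 runs it "BY visit istest variant", and "Missing data will not be replaced".
- **Late visits.** SAP Section 4.3.1: "The analyses of secondary endpoints at the specified time points will be performed as described in Section 4.2.2". The Day 91 and Day 181 fits therefore contain no Day 29 titer.
- **Analysis sets.** SAP Section 4.3 presents the final immunogenicity results for both the Exposed Set (ES) and the PPS. No censoring rule is stated for the ES.
- **Titer and protection.** Protocol Section 4.2.1, on earlier efficacy studies: "Vaccine efficacy increased with the neutralizing titer in each of these analyses of mRNA vaccines".
- **Estimand.** Protocol Section 3 refers to Section 9 for the handling of intercurrent events, and SAP Section 1.1 refers to its Section 3. Both places state the censoring rule but not the quantity to be estimated.

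**The concern.** Removing titers after infection suggests interest in the titer that would have been seen without infection. The mean of those left estimates that only if infection is unrelated to titer, given the model covariates. The protocol's own rationale points the other way: low responders should be infected, and so removed, more often.

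The pre-dose titer does not repair this. Infection risk follows the post-dose response, which the pre-dose titer predicts only in part. The least-squares means are also evaluated at the mean pre-dose titer of those still in that visit's model.

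The information that would help is already collected. PPS entry requires a Day 29 titer, and a missing Day 29 sample excludes the participant (SAP Section 6.1.3). Nearly everyone censored later therefore has a Day 29 value that the late-visit models ignore. At stake are the PPS persistence results (GMT and GMI at Days 91 and 181) and some precision in the late ratios.

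**Working it through.** **Inputs from the documents.** "83 participants will be enrolled in each of the 5 groups", "randomized in a 1:1:1:1:1 ratio" (5 × 83 = 415). "Confidence intervals (CIs) will use 95% confidence levels". The ratio reference value is 0.67, and −log10(0.67) = 0.174. The SD, assumed ratio and power behind 83 are redacted, so that figure cannot be reproduced. For orientation only: with a true ratio of 1 and SD 0.40 log10, 0.174 / (0.40 × √(2/83)) − 1.96 = 0.84, which is 80% power.

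**Assumed inputs (none are in the documents).** SD 0.5 log10; correlation 0.8 between adjacent post-dose visits and 0.6 with pre-dose; 10-30% of controls infected by Day 181; infection odds ratio per 10-fold lower titer of 1, 2.7 or 10.

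**Step 1, hand check of the GMT bias.** With logistic risk of slope β per log10 titer and proportion p infected, the mean log10 titer of those left shifts, to first order, by β × p × r × σ². Here r is the correlation between the titer driving the risk and the Day 181 titer. For odds ratio 2.7, β = ln 2.7 ≈ 1. With p = 0.20, r = 0.8 and σ² = 0.25, the shift is 0.040 log10, and 10^0.040 = 1.10. At p = 0.10 and 0.30 it gives 1.05 and 1.15. The approximation is rough at odds ratio 10, so the simulation is used there.

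**Step 2, simulated inflation of the Day 181 control GMT** (by-visit ANCOVA, 300,000 per arm; ranges cover risk driven by the last measured or by the current titer):

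| Infected | Odds ratio 1 | Odds ratio 2.7 | Odds ratio 10 |
|---|---|---|---|
| 10% | ×1.00 | ×1.05 | ×1.10-1.13 |
| 20% | ×1.00 | ×1.09-1.11 | ×1.19-1.25 |
| 30% | ×1.00 | ×1.15-1.18 | ×1.29-1.37 |

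Adjustment for pre-dose titer changes little: in one 30%, odds ratio 2.7 run, the raw inflation was ×1.149 and the adjusted ×1.153.

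**Step 3, GMI.** This was not simulated in the table. Those left also have higher pre-dose titers, so part cancels. To first order, with equal SDs, the GMI shift is β × p × (0.8 − 0.6) × 0.25 = 0.010 log10 at 20% infected, or ×1.02 where the GMT shows ×1.10.

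**Step 4, simulated Day 181 GMT ratio** (simulation error about 0.003):

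| True ratio | Odds ratio 2.7 | Odds ratio 10 |
|---|---|---|
| 1.00 | 1.00 | 1.00 |
| 0.80 | 0.80-0.81 | 0.81-0.82 |
| 0.67 | 0.672-0.679 | 0.686-0.701 |
| 0.50 | 0.504-0.512 | 0.52-0.55 |

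**Step 5, joint repeated-measures model of Days 29, 91 and 181.** If risk depends on the last measured titer, the GMT is recovered (×1.00), as are ratios of 0.67 and 0.80 within simulation error. If risk depends on the unmeasured current titer, some bias remains: GMT ×1.01-1.10 instead of ×1.05-1.37, and a true 0.67 is estimated as 0.673-0.684 instead of 0.676-0.701.

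**Step 6, precision at 83 per arm** (4,000 replicates; SD of the Day 181 log10 ratio):

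| Titers kept | By visit | Joint | Variance ratio |
|---|---|---|---|
| 81% | 0.0692 | 0.0666 | 0.925 |
| 72% | 0.0738 | 0.0695 | 0.886 |
| 63% | 0.0789 | 0.0720 | 0.832 |
| 50% | 0.0903 | 0.0795 | 0.775 |

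The variance reduction is therefore about 7%, 11%, 17% and 23%. Hand check of the 72% row: 83 × 0.72 ≈ 60 per arm; residual SD 0.5 × √(1 − 0.6²) = 0.40; 0.40 × √(2/60) = 0.073.

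**Step 7, bias against standard error.** For a single-arm adjusted GMT with 60 left, the SE is 0.40/√60 = 0.052 log10. A 10% inflation is log10(1.10) = 0.041, about 0.8 SE. For the ratio, the largest shift at 0.67 is log10(0.701/0.67) = 0.020, about 0.2-0.3 of the SEs in Step 6.

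**The case against.** The strongest reply is that little hangs on these estimates. They are secondary, Part A only, in a study that SAP Section 2 describes as having no hypothesis testing. SAP Section 2 ties the p-values against 0.67 to the primary endpoints, and the committee recommendation on dose uses Day 29 interim data. Reporting available data without replacement is a stated choice, and as a description of uncensored participants the planned GMT is not biased at all. All of this stands. It limits the importance of the point but does not remove it: where the emphasis is on estimation, a late GMT that will be read as persistence should say what it estimates.

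Four stronger readings are tempting, and the documents do not support them:

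- **That all late Part A titers are censored.** The rule belongs to the PPS; the ES is also reported and, as written, keeps post-event titers. The ES does not correct the PPS, because infection and vaccination themselves raise titers, so it answers a different question.
- **That comparisons with the control are materially distorted.** The ratio bias is nil when arms are equal and small against its standard error otherwise.
- **That censoring for COVID-19 vaccination also selects high responders.** Nothing in the documents links later vaccination to titer. If they are unrelated, it costs precision only.
- **That a joint model removes the bias.** It does so only if censoring depends on observed titers.

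**Conclusion.** The point holds for the Part A PPS at Days 91 and 181. If infection is more likely at low titers, as Protocol Section 4.2.1 suggests, late GMTs read as the titer without infection are too high: about 5-18% at an odds ratio of 2.7 per 10-fold lower titer, and up to 37% at an odds ratio of 10. GMIs are too high by a smaller amount. Ratios are pulled toward 1 only when arms differ, by at most about 0.03 at true ratios of 0.67-0.80 and 0.05 at 0.50. Near 0.67 that direction is anti-conservative.

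Every magnitude rests on an assumed SD, correlations, attack rate and slope; the documents give none, and with no link between titer and infection the bias is zero. It would be wrong to infer that the Day 29 primary results, dose selection or Part B are compromised. This is a worthwhile, low-cost improvement to a secondary analysis.

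**What to change.** 1. For the Part A PPS, fit one repeated-measures model per strain to log10 titers at Days 29, 91 and 181. Include group-by-visit, log10 pre-dose titer-by-visit, country, prior COVID-19 and age group, with unstructured covariance. Report Day 91 and Day 181 GMT, GMI and ratios from it beside the by-visit ANCOVA. Day 29 estimates stay as planned.
2. State the Day 91/181 estimand separately for the ES and the PPS, including how infection and COVID-19 vaccination are handled in each.
3. Add a sensitivity analysis for departures from missing-at-random, since risk may follow the unmeasured current titer.
4. Record the addition in SAP Section 4.8, because Protocol Section 9.3.3 names ANCOVA for these endpoints.

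The cost is SAP wording and modest programming, with no new data. The downside is reliance on missing-at-random given observed titers. That is a weaker assumption than the by-visit fit needs, but still an assumption.

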### 9.3.3. Secondary endpoints analyses

The secondary endpoints detailed in **Table 5 for Part A** will be analyzed as described in the SAP. Listings will be provided, and graphical presentations will be considered as needed. In addition to descriptive statistics for continuous variables, CIs and quartiles will also be provided for continuous immunogenicity variables. Seroresponse rate with 95% CI, GMT of specific Ab with corresponding 95% CI and GMI from baseline of specific Ab with corresponding 95% CI will also be provided by group. The GMT, the GMI, and their 95% CI in each group will be analyzed using an ANCOVA *on  $\log_{10}$ -transformed tier* with vaccine group, country, previous known COVID-19 infection (yes defined by self-reporting or positive N protein at pre-vaccination, no), age (< 65 years,  $\geq$  65 years) and  $\log_{10}$ -transformed pre-dose titer as fixed effects.

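### Default LSMEANS gives per-arm adjusted GMTs and GMIs for an equal-weighted covariate mix, which differs from the enrolled mix unless enrolment is balanced; the GMT ratio is unaffected

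*SAP*

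**What the plan says.** SAP 4.2.2 fits one additive ANCOVA per visit and variant, printed under Table 2 as "MODEL log = trt country priorcovid agegroup logbase". Treatment, country, prior COVID-19 and age group are CLASS factors, and log10 pre-dose titer is a covariate. The procedure line is "PROC GLM DATA=is ALPHA=0.05", and the only estimation statement is "LSMEANS trt / CL".

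The listing is introduced with "The following SAS code will be used for computation of GMT ratio". The text of 4.2.2 also draws the per-arm results from that fit: "The adjusted GMT and GMI in each group will be obtained from the same model with 95% CI". Protocol 9.3.3 agrees: "The GMT, the GMI, and their 95% CI in each group will be analyzed using an ANCOVA". The between-arm comparison "will be based on group contrast from an ANCOVA model on log10-transformed anti-neutralizing titer", and it carries a "p-value for the null hypothesis that group GMT ratio is below 0.67".

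Neither document names a reference population for the adjusted per-arm means or gives a weighting option. SAP 4.1.1 separately plans unadjusted GMTs and GMIs with t-based CIs.

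**The concern.** With no weighting option, PROC GLM averages the predicted response over the levels of each CLASS factor with equal coefficients. Half the weight goes to participants aged 65 or over, half to those with prior COVID-19, and each country gets the same share however few it enrolled. Baseline titer is held at its mean in the data.

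The adjusted GMT is then standardised to a mix that software chose rather than one the plan chose. The adjusted GMI has a further mismatch: an equal-weighted post-dose mean is set against a baseline that reflects the enrolled mix. A sparse level, such as a small country, contributes heavily to the standard error.

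GMT is the population summary of the primary immunogenicity endpoint in both parts, and GMI is a Part A secondary endpoint. Readers would see an adjusted and an unadjusted GMT for each arm. The two could differ purely through weighting, and nothing in the SAP would explain why.

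**Working it through.** **Inputs from the documents.** There are 83 participants per arm: 3 × 83 = 249 in Part B and 5 × 83 = 415 in Part A, which match the stated totals. The model is additive with no treatment interaction. Protocol 6.3 stratifies by country, prior COVID-19 and age and sets no quota. Protocol 10.1.4 allows enrolment targets to be redistributed between sites across countries.

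**Inputs that are assumed.** These are the number and shares of countries, the shares with prior COVID-19 and aged 65 or over, and the log10 effects of the factors. The documents give none of them. One pointer is SAP 4.6.1, which makes subgroup analyses conditional on 15 participants per arm per level. The SAP thus allows that a level may hold less than 15/83 = 18% of an arm.

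**Step 1: the comparison does not move.** The LS-mean for arm t is L_t·θ, where L_t has a 1 for arm t followed by the covariate weights. Those weights are identical for every arm, so L_t − L_1 is zero on country, prior COVID-19, age and baseline. Equal and observed weights therefore give the same ratio, CI and p-value. One simulated three-arm data set shows this:

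| Weights | Adjusted GMTs | CI factor (×/÷) | Ratios to arm 1 |
|---|---|---|---|
| Equal | 376 / 321 / 292 | 1.29-1.33 | 0.852, 0.775 |
| Observed | 416 / 355 / 322 | 1.25 | 0.852, 0.775 |

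The standard error of the contrast between arms 3 and 1 was 0.0692 under both. Each GMT is about 10% lower with equal weights (376/416 = 0.90).

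**Step 2: width of the per-arm CI.** With observed margins the variance of an adjusted mean is close to σ²/83. If the factors are roughly independent, moving to equal weights multiplies the SE by approximately

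sqrt(1 + (D_country + D_prior + D_age)/arms)

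For a two-level factor with share p, D = (0.5 − p)²/[p(1 − p)]. For K countries with shares s_k, D = Σ 1/(K² s_k) − 1. The residual SD cancels.

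- *All margins 50/50:* every D is 0, so the ratio is 1.00.
- *Countries 70/30, prior COVID-19 70%, aged 65 or over 25%:* 0.190 + 0.190 + 0.333 = 0.714. Part B: sqrt(1 + 0.714/3) = 1.11. Part A: sqrt(1 + 0.714/5) = 1.07.
- *Countries 90/10, prior COVID-19 80%, aged 65 or over 20%:* 1.778 + 0.5625 + 0.5625 = 2.903. Part B: 1.40. Part A: 1.26.
- *Countries 90/5/5, prior COVID-19 85%, aged 65 or over 15%:* 3.568 + 0.961 + 0.961 = 5.489. Part B: 1.68. Part A: 1.45.

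The full ANCOVA algebra over 200 simulated designs per scenario gives slightly larger ratios, because realised shares vary and factors overlap by chance:

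| Assumed shares | Part B | Part A |
|---|---|---|
| Balanced | 1.01 | 1.00 |
| 70/30, 70%, 25% | 1.12 | 1.08 |
| 60/30/10, 70%, 25% | 1.22 | 1.14 |
| 90/10, 80%, 20% | 1.46 | 1.30 |
| 90/5/5, 85%, 15% | 1.82 | 1.54 |

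If only age is unbalanced, at 18%, the ratios are 1.12 in Part B and 1.07 in Part A.

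**Step 3: shift of the per-arm GMT.** The shift on the log10 scale is Σ (equal weight − observed share) × effect, and it is the same in every arm.

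- *Prior COVID-19 80% with effect +0.10, aged 65 or over 20% with effect −0.10, no country effect:* (0.5 − 0.8)(0.10) + (0.5 − 0.2)(−0.10) = −0.06, and 10^−0.06 = 0.87, about 13% lower.
- *Same shares, effects +0.15 and −0.10, and a country with a 10% share and effect +0.10:* −0.045 − 0.030 + 0.040 = −0.035, and 10^−0.035 = 0.92, about 8% lower.
- *Balanced margins:* no shift.

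**Step 4: GMI.** Fitting the same model to log post-dose minus log pre-dose titer lowers only the baseline coefficient by 1. Its LS-mean equals the post-dose LS-mean minus the mean log10 pre-dose titer. Both routes give the same GMI and carry whichever factor weights are used.

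**The case against.** The case on the other side has real force.

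- *No planned inference is touched.* This is correct (step 1). The shift is common to all arms, so their ranking and the between-arm reading are unchanged.
- *The intervals are not wrong.* This is also correct. A reader might infer from the wider CIs that they are too wide, but they have the right coverage for the equal-weighted mean. They are wider only relative to a target the SAP does not name.
- *The size is unknown.* This stands. A reader might infer that the adjusted GMTs certainly describe a population the trial did not enrol. The documents do not support that, because with balanced margins the effect vanishes.
- *Unadjusted GMTs and GMIs are planned in SAP 4.1.1.* They describe the analysed participants and limit the harm. They do not explain why the adjusted values might differ.
- *The code is introduced for the GMT ratio and prints no GMI step.* True, but 4.2.2 takes the adjusted GMT and GMI from the same model, and no other estimation statement is given.
- *Equal weighting is a legitimate standardisation, and observed margins would vary by visit and analysis set.* This is a fair trade-off but a minor one. If the aim is to describe the participants analysed, the weights should follow them.

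**Conclusion.** The point holds for the per-arm adjusted GMT and GMI only. As printed, the plan leaves their reference population to a software default that weights country, prior COVID-19 and age levels equally. Unless all three factors happen to be balanced, the values refer to a different mix from the one enrolled.

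The log-scale CI, relative to observed margins, is about 0% wider under balance. Under moderate to marked imbalance it is 12%-46% wider in Part B and 7%-30% wider in Part A; with two countries at 5% each it reaches 82% and 54%. The common GMT shift runs from 0% to roughly -13%. All of these sizes rest on assumed shares, and the shift also on assumed effects of 0.10 to 0.15 log10.

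A reader might go further and infer that the non-inferiority evidence against 0.67 is biased or loses precision. The additive model rules that out, because the weights cancel from the contrast.

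**What to change.** 1. Add the observed-margins option to the statement in 4.2.2, so that it reads `LSMEANS trt / CL OM;`. Pass the procedure only the records analysed at that visit and for that variant, so that the margins are those of the analysed set.
2. State in 4.2.2 that adjusted GMTs are standardised to the observed distribution of country, prior COVID-19 and age in the analysed set.
3. Specify the adjusted GMI on the same margins: either the same model fitted to log10 post-dose minus log10 pre-dose titer, or the observed-margin mean minus the mean log10 pre-dose titer.

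The cost is one SAS option and two or three SAP sentences. The GMT ratio, its CI, its p-value and the sample size do not change. If the sponsor prefers equal weighting, the SAP should say so and name the resulting reference mix.
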